3.3 Analysis populations

Intention to Treat population: this population includes all aSAH patients randomized except those who were a post-randomization exclusion, withdrew consent, or were lost to follow up.

Per Protocol Population: this population is the intention to treat population except those who had a protocol violation (as defined in 3.2).

The primary analysis of all outcomes will be conducted on the Intention to Treat population. A secondary, sensitivity analysis, on the Per Protocol population will also be conducted and reported separately, accompanied by a description of the population characteristics, in the supplement.

Section 4 – Trial Population

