1.2 Objectives

Our primary objective:

To evaluate the effect of a liberal (Hb trigger $\leq 100\text{g/L}$) versus a restrictive (Hb trigger $\leq 80\text{g/L}$) RBC transfusion strategy in acute aSAH patients with anemia ($\text{Hb} \leq 100\text{g/L}$) on patient-oriented functional neurologic outcome at 12 months.

Our secondary objectives:

To evaluate the effect of a liberal versus a restrictive RBC transfusion strategy on: a) 12-month overall function; b) quality of life at 12 months; c) mortality; d) delayed cerebral ischemia and radiographic vasospasm and e) clinically relevant stroke at hospital discharge on routine brain imaging.

Our tertiary objectives:

To evaluate the effect of a liberal versus a restrictive RBC transfusion strategy on lowest daily hemoglobin levels, RBC transfusions, expected and transfusion-related adverse events, mechanical ventilation and ICU and hospital length of stay.

Section 2: Study Methods

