2.6 Timing of outcome assessment

Primary outcome:

- a) Modified Rankin Scale (mRS) score [12 months]

Secondary outcome:

- a) Functional Independence Measure (FIM) [12 months]
- b) EuroQOL Quality of Life Scale 5-Dimension 5-Level (EQ-5D-5L) and visual analogue scale (VAS) [12 months]
- c) Mortality [in-hospital]
- d) Delayed Cerebral Ischemia and Radiographic Vasospasm [over the first 21 days in hospital]
- e) New cerebral infarction [in-hospital]

Tertiary outcome:

- a) Lowest daily hemoglobin level [over the first 21 days in hospital]
- b) Proportion of patients who have an RBC Transfusion [over the first 21 days in hospital]
- c) Expected and transfusion-related adverse events [over the first 28 days in hospital]
- d) Need for and duration of mechanical ventilation [in-hospital]
- e) Length of stay [in-hospital]

Section 3: Statistical Principles

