4.2 Withdrawal/Follow-up

When a patient is lost to follow-up their 12-month mRS score will be missing, therefore, this patient cannot be included in the analysis of the primary outcome. Whenever possible, these patients will be included in the secondary outcome analyses.

No data will be analysed for patients who withdraw consent, but such patients will be listed in the CONSORT diagram.

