5.2 Analysis Methods

Unless otherwise specified, all analyses will be completed on the intention to treat population (see section 3.3). Given the pragmatic nature of the trial, and possible variations in practice from centre to centre, randomization was stratified by centre. As such, all primary analyses are adjusted for centre and sex as aSAH predominantly affects females. In summary, unless stated otherwise below, all parametric analyses will be conducted using Generalized Linear Mixed Models (GLMM) with fixed effects for treatment and sex, and a random effect for centre. Non parametric median estimates will be conducted using quantile regressions adjusting for site and sex. A summary of the proposed analyses is presented in Table 4.

Primary Outcome:

Primary analysis:

- The main statistical analysis will be done on the intention to treat population with a binomial GLMM with log-link function and reported as a risk ratio with corresponding 95% confidence interval.

Secondary analysis:

- For the primary outcome a proportional odds analysis, will additionally be conducted. The proportional odds assumption will be tested using the Brant-Wald test at the alpha level of 5%.

Sensitivity analysis:

Sensitivity analysis of the primary outcome will be tested in 4 ways:

- Further adjusted with WFNS and age as additional fixed effects
- We chose dichotomized mRS scores as the results of the analysis are simple to understand and interpret, but the cut-off is arbitrarily chosen and information is lost by dichotomization. Therefore, we will repeat the primary analysis with unfavorable neurologic outcome defined as mRS ≥ 3 rather than ≥ 4 .
- Per protocol analysis (see section 3.3)
- Best case-worst case scenario. In this sensitivity analysis of the primary outcome, we will include randomized patients in which the primary outcome is missing – e.g. withdrawal or lost to follow-up. Patients who were randomized in error will be excluded. Two scenarios will be considered:
 - Best-case scenario: a favourable outcome will be imputed for those in the liberal transfusion strategy arm with missing primary outcome, and unfavourable outcome to those in the restrictive transfusion strategy arm with missing primary outcome.
 - Worst-case scenario: an unfavourable outcome will be imputed for those in the liberal transfusion strategy arm with missing primary outcome, and a favourable outcome to those in the restrictive transfusion strategy arm with missing primary outcome.

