* Unless otherwise stated, all analyses will be conducted on the Intention to treat population: includes all aSAH patients randomized except those who were a post-randomization exclusion, withdrew consent, or were lost to follow up.

** Adjustments for all listed analyses unless otherwise specified

† Per-protocol population includes the intention to treat population (all aSAH patients randomized except those who were a post-randomization exclusion, withdrew consent, or were lost to follow up), but excludes those who had a protocol violation.

‡ In the best-case scenario: a favourable outcome will be imputed for those in the liberal transfusion strategy arm with missing primary outcome, and unfavourable outcome to those in the restrictive transfusion strategy arm with missing primary outcome. In the worst-case scenario: an unfavourable outcome will be imputed for those in the liberal transfusion strategy arm with missing primary outcome, and a favourable outcome to those in the restrictive transfusion strategy arm with missing primary outcome.

CI – confidence interval; DCI – delayed cerebral ischemia; EQ-5D-5L VAS – EuroQOL 5 dimensions 5 levels Visual Analogue Scale; FIM – Functional Independence Measure; GLMM – Generalized linear mixed methods; ICU – Intensive Care Unit; IQR – Interquartile Range; mRS – modified Rankin Scale; RBC – Red blood cell; WFNS – World Federation of Neurological Surgeon

Section 6 – References

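### SAP 3.3 removes patients lost to follow-up from the population used for every outcome; 4.2 restores them for secondary outcomes only, so the in-hospital tertiary outcomes have no written exception

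*SAP*

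**What the plan says.** - SAP 3.3 defines the Intention to Treat population as "all aSAH patients randomized except those who were a post-randomization exclusion, withdrew consent, or were lost to follow up". It then states: "The primary analysis of all outcomes will be conducted on the Intention to Treat population". No qualifier is attached. The Per Protocol population is this set less patients with a protocol violation, so it inherits the same exclusion.
- SAP 4.2 ties loss to follow-up to a missing 12-month mRS and takes those patients out of the primary analysis. It continues: "Whenever possible, these patients will be included in the secondary outcome analyses". Tertiary outcomes are not named. On consent withdrawal it agrees with 3.3: "No data will be analysed for patients who withdraw consent".
- The Table 4 footnote says: "Unless otherwise stated, all analyses will be conducted on the Intention to treat population". SAP 5.2 gives the same default, with a similar opening qualifier and a pointer to 3.3. Both Table 4 population footnotes restate the exclusion of lost patients, and neither points to 4.2.
- The tertiary objectives in SAP 1.2 concern the effect of the strategy "on lowest daily hemoglobin levels, RBC transfusions, expected and transfusion-related adverse events, mechanical ventilation and ICU and hospital length of stay". SAP 2.6 confines these outcomes to the first 21 or 28 days in hospital or to the hospital stay.
- Protocol 6.6 has adverse events and the other secondary measures recorded prospectively at the sites. Protocol 9.4 describes loss in terms of repeated failed attempts to make contact, in a section about the 6- and 12-month assessments.

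**The concern.** A patient who cannot be reached at 12 months has normally already supplied hospital data: survival to discharge, DCI, infarction, transfusions, adverse events, ventilation and length of stay. Removing that patient from the hospital outcomes discards recorded data because of an event after the outcome window closed. For the primary outcome the removal cannot be avoided without imputation. For the hospital outcomes it can.

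Denominators are also at stake. An analyst following 3.3 and one following 4.2 would report different numbers for hospital mortality, DCI, vasospasm and infarction. Protocol 6.10 gives the analysis to a statistician outside the study team, who has to rely on the written text.

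**Working it through.** **Rules side by side, for a patient lost to follow-up**

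| Outcome | SAP 3.3 alone | With SAP 4.2 as an exception |
|---|---|---|
| Primary (12-month mRS) | out | out: no score, and 5.3 does not impute outcomes |
| Hospital mortality, DCI, vasospasm, infarction | out | in |
| 12-month mortality | out | in, but this matters only for patients known to be alive without an mRS; a patient found dead scores 6 and is not missing |
| Six tertiary rows | out | not addressed, so out if read literally |

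**Inputs.** From SAP 2.3: 740 patients, 40% versus 30%, 80% power, 5% type I error, 3% loss. From SAP 3.1: two-sided inference. From Protocol 9.4: loss below 1% in similar populations and follow-up above 95% in the team's own experience, used here as a 1% to 5% range. From Protocol section 5: 35% mortality (range 20% to 67%, no time point given). The documents give no hospital mortality for this trial, so 20% and 35% are assumptions.

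**The plan's own figure.** n per arm = [1.960 × √(2 × 0.35 × 0.65) + 0.842 × √(0.40 × 0.60 + 0.30 × 0.70)]² / 0.10² = 356, or 712 in total. Then 712 / 0.97 gives 735, which agrees with 740 after modest rounding up. This point does not dispute the sample size.

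**Patients affected.** 740 × 0.03 = 22.2. The range is 740 × 0.01 = 7.4 to 740 × 0.05 = 37.

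**Hospital mortality.** An in-hospital death has mRS 6, so lost patients are hospital survivors. Removing a fraction L of an arm turns mortality m into m / (1 − L).

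| Assumed m | L = 1% | L = 3% | L = 5% |
|---|---|---|---|
| 20% | 20.2% | 20.6% | 21.1% |
| 35% | 35.4% | 36.1% | 36.8% |

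The risk ratio (liberal to restrictive) is multiplied by (1 − L_res) / (1 − L_lib). Equal loss gives exactly 1. An assumed imbalance of 5% versus 1% gives 0.99 / 0.95 = 1.042 or 0.95 / 0.99 = 0.960, a shift of 0.041 on the log scale. With 370 per arm and a true ratio of 1:

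- At 20% mortality (74 deaths per arm), SE = √(2 × (1/74 − 1/370)) = 0.147, 95% CI about 0.75 to 1.33. The shift is 0.041 / 0.147 = 0.28 SE.
- At 35% mortality (129.5 deaths per arm), SE = 0.100, 95% CI about 0.82 to 1.22. The shift is 0.41 SE.

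**Adverse-event row.** The bias in each arm is L × (rate in retained − rate in lost), and the shift in the between-arm difference is the difference of the two biases. All gaps below are assumptions.

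- 3% loss in both arms, same gap in both: no shift.
- 3% loss in both arms, gaps of 10 and 20 points: 0.6 − 0.3 = 0.3 points.
- 5% versus 1% loss, same gap of 10 or 20 points in both arms: 0.04 × 10 = 0.4 points, or 0.04 × 20 = 0.8 points.

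**The case against.** The best reply is that the SAP already settles most of this. Section 4.2 is the only passage written specifically for lost patients, and the qualifiers in 5.2 and the Table 4 footnote leave room for such a rule. A reader of the whole SAP would probably apply 4.2 to the secondary outcomes. That stands. What remains there is an unqualified sentence in 3.3 that says otherwise, with no cross-reference.

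For the tertiary rows, the reply is that everything turns on the word secondary in 4.2. The protocol abstract listed RBC units, lowest hemoglobin, transfusion complications, ventilation and length of stay as secondary, and Protocol 6.6 groups adverse events with the secondary measures. The SAP later moved these to tertiary, so 4.2 may carry the older meaning. That is plausible, and nothing shows an intention to keep lost patients for infarction but drop them for transfusion. A reader might infer that the sponsor means to discard this material; the documents do not support that. They leave the intent unstated, and the literal text has no exception.

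A reader might also infer that safety reporting as a whole is compromised. It is not. SAP 5.4 has reportable unexpected serious adverse events described with the main results, with no population limit, and SAP 2.4 records twice-yearly adverse-event reports to the DSMB. The safety effect is confined to the one row for expected and transfusion-related events.

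Finally, SAP 5.3 already promises the frequency of missing data, which goes part of the way towards a denominator for each outcome.

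**Conclusion.** A minor inconsistency that should be corrected. For secondary outcomes, 3.3 contradicts 4.2, although 4.2 is probably meant to prevail. For the six tertiary rows, the written rule excludes recorded in-hospital data, possibly through inherited wording.

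The size is about 22 of 740 patients at the planned 3% loss; the documents do not report actual losses. Applying 3.3 literally slightly overstates hospital mortality in each arm and leaves the risk ratio unchanged if loss is equal across arms. Even an assumed 5% versus 1% imbalance moves the log risk ratio by less than half a standard error. For adverse events it would be too strong to say that equal loss removes the bias: that holds only if the gap between retained and lost patients is the same in both arms. Lowest hemoglobin is only graphed by group.

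It would also be wrong to infer that the primary result is at risk. A lost patient has no 12-month mRS under either section, outcomes are not imputed in the main analysis, and the best-case and worst-case scenarios bring such patients back for the primary outcome. SAP 3.1 reports a p-value only for that outcome, so what is affected elsewhere is estimates, intervals and denominators.

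**What to change.** - Delete the lost-to-follow-up exclusion from SAP 3.3 and from both Table 4 population footnotes.
- State that each secondary and tertiary outcome, including adverse events, is analysed as allocated in all randomised patients with that outcome observed, except post-randomisation exclusions and patients who withdrew consent.
- Keep the 4.2 rule that patients without a 12-month mRS are not in the primary analysis, and extend its next sentence to tertiary outcomes.
- Cross-refer 3.3 to 4.2, and report the denominator for each outcome.
- Note the knock-on effect: the Per Protocol population is built on Intention to Treat, so lost patients without a violation would enter any secondary or tertiary analysis run on it. Its primary-outcome analysis does not change.

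The cost is SAP wording, to be settled before database lock. It needs no new data, no extra patients and no change to the sample size.

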- 3 **SAHaRA Canadian multicenter observational study:** We conducted a multicenter retrospective cohort study of aSAH patients (n=527) admitted to any of 4 academic centers across Canada between 1 January 2012 and 31 December 2013. The primary objective was to describe a Canadian aSAH population with respect to both anemia incidence and RBC transfusion practices.^{23,28} Anemia (hemoglobin \leq 100g/L) prevalence was 51.8% and the median pre-transfusion hemoglobin in the 19% of the cohort transfused was 79g/L (IQR: 74-93). (Supported by peer-reviewed grants from Depts of Medicine/Critical Care, uOttawa, presented at an international conference^{23,28})

CIHR/CBS-funded pilot RCT (NCT02483351): We have successfully completed enrolment into the SAHaRA internal pilot RCT, the principal (SE) and SAHaRA investigators, in collaboration with the CCCTG, have demonstrated successful recruitment, adherence to intervention, and trial protocol feasibility. There have been 2 interim analyses and DSMB reviews which supported continuation without modification (60 of 60 patients), we demonstrated a recruitment rate of >1 patients/center/month. Adherence to treatment allocation was 92% (15 deviations and 3 violations from 97 transfusion episodes). The difference of mean pre-transfusion hemoglobin between groups was 21.1 ± 6.5 g/L. RBC transfusion occurred within 6 hours of trigger hemoglobin in 84.5% of transfusions and within 11 hours in 100%. We have created the necessary infrastructure, procedures and network to successfully conduct the full trial. (Funded CIHR/CBS-201507-SE-343843; Protocol manuscript published²⁹)

With this above work, the network-building and partner collaborations we have established, we are perfectly positioned to complete the SAHaRA trial.

6 Approach and Methods

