2.1 Trial Design

SAHaRA is a multicenter pragmatic randomized trial in patients with aSAH that compares the effect of a liberal to a restrictive RBC transfusion strategy on the combined rate of death and severe disability at 12 months. Our PROBE (prospective, open-label, blinded endpoint) approach has been informed by and tested in our CIHR/CBS-funded pilot RCT.¹⁴

Trial interventions

Eligible patients are randomized to either a restrictive or a liberal RBC transfusion strategy. Hemoglobin is checked at least daily while on protocol up to and including Day 10 post aSAH or while in an ICU/HAU (high-acuity unit), and then at the discretion of the primary clinical team.

Restrictive RBC Transfusion Strategy: For patients randomized to this group, an RBC transfusion is permitted once a hemoglobin level of ≤ 80 g/L is observed over the first 21 days following aSAH. RBC transfusion below the threshold is not mandatory, rather “usual care” prevails, with the decision and timing of transfusion left to the discretion of the treating team.

Liberal RBC Transfusion Strategy: An RBC transfusion is triggered by a hemoglobin level of ≤ 100 g/L over the first 21 days in hospital following aSAH. Transfusion in this arm is mandatory.

Both Groups: All RBC transfusion orders are single unit unless the patient has active blood loss associated with hemodynamic instability (see section 9.1 of the protocol – see Appendix). In stable non-bleeding patients, a second unit of RBCs is given if a measured post-transfusion hemoglobin level remains below the patient’s assigned threshold. Protocol adherence and violations are discussed in section 9.1 of the protocol (see Appendix).

Duration of the intervention

The allocated transfusion strategy is applied from the time of randomization to 21 days after the original bleed, death or hospital discharge, whichever comes first. The first 21 days following aSAH represent the period of greatest vulnerability to the direct consequences of aSAH, and the sequelae, including DCI, that follow.

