3.2 Adherence and protocol deviations

The study adherence is measured in 2 domains:

1) Adherence to allocated transfusion threshold: This occurred if an RBC transfusion is given only in response to the transfusion threshold being crossed with the last hemoglobin measure prior to transfusion being below the appropriate threshold. *Non-adherence* will be considered to have occurred if a) an RBC transfusion occurs before a transfusion threshold is crossed; or b) in the liberal arm, a transfusion is not given following a threshold crossing. Non-adherence will be

considered a *deviation* if: 1) the early transfusion occurs within 5 g/L above the allocated threshold (e.g., ≤ 105 g/L for the liberal arm or ≤ 85 g/L for the restrictive arm) or, 2) in the liberal arm, an RBC transfusion does not occur for a hemoglobin measure up to 5 g/L below the threshold (i.e.: a transfusion does not occur for a hemoglobin of 95-100 g/L). All other threshold event non-adherences will be considered a protocol violation. Details on non-adherence (date and hemoglobin level prior to transfusion) and reasons for non-adherence will be recorded. In the event of an active blood loss associated with hemodynamic instability, as defined by the treating team, standard resuscitation practices prevail (including blood product administration). Transfusion under this circumstance would not be a protocol violation. The allocated transfusion strategy will resume when hemodynamic stability is achieved and it is the opinion of the treating team that active bleeding has stopped. Transfusion outside of hemoglobin thresholds for symptomatic anemia (as assessed by the bedside team) will be recorded, but not considered a protocol violation.

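### The per-protocol analysis drops any patient with a violation, under rules that differ by arm, yet adjusts only for centre and sex; it may be confounded by severity, in an unknown direction

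*SAP*

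**What the plan says.** SAP 3.3 defines the per-protocol population by removal: "this population is the intention to treat population except those who had a protocol violation (as defined in 3.2". The footnotes to Table 4 repeat this, and neither place sets a minimum number of violations.

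SAP 3.2 defines violations. One route to non-adherence exists in a single arm: "in the liberal arm, a transfusion is not given following a threshold crossing". In the restrictive arm there is no counterpart, since "RBC transfusion below the threshold is not mandatory" (SAP 2.1). Early transfusion counts in both arms and becomes a violation when the hemoglobin is more than 5 g/L above the allocated trigger. A liberal-arm omission at 95-100 g/L is only a deviation and removes nobody. Transfusion for symptomatic anemia, or for active bleeding with instability, is exempt.

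On the model, SAP 5.2 says "all primary analyses are adjusted for centre and sex as aSAH predominantly affects females". Table 4 lists centre and sex, with the footnote "Adjustments for all listed analyses unless otherwise specified", and specifies nothing else for the per-protocol analysis. Severity enters elsewhere, as its own sensitivity analysis: "Further adjusted with WFNS and age as additional fixed effects". That item is listed beside the per-protocol analysis and not combined with it.

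On standing, SAP 3.3 makes intention-to-treat primary and adds: "A secondary, sensitivity analysis, on the Per Protocol population will also be conducted and reported separately, accompanied by a description of the population characteristics". The results go in the supplement.

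**The concern.** Whether a patient stays in the per-protocol set is decided by events over as much as 21 days after the bleed, and the rules are not the same in the two arms. A patient qualifies with hemoglobin at or below 100 g/L, so a liberal-arm patient has already met that arm's trigger at entry. A restrictive-arm patient may never reach 80 g/L. The retained groups are therefore not comparable by design.

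Severity is the obvious candidate confounder. In its subgroup rationale, SAP 5.2 links a poorer admission grade both to anemia and to a bad outcome. The SAP also already treats WFNS and age as worth adjusting for, but does so on the randomised set and not on the set where randomisation has been broken.

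The per-protocol result is one of four named sensitivity analyses of the primary outcome. As planned, a reader could not tell whether its agreement or disagreement with the main result reflects treatment or selection.

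**Working it through.** **Plan's own figures.** The plan gives no figure for the per-protocol analysis. Its sample size does reproduce: 40% vs 30%, two-sided 5%, 80% power, no continuity correction, gives 356 per arm, 712 in total, and 712/0.97 = 735 against the stated 740. With 3% loss, 740 × 0.97 / 2 ≈ 359 per arm are analysed.

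**Violation rate.** Protocol 5.3 reports "15 deviations and 3 violations from 97 transfusion episodes" in the 60-patient pilot: v = 3/97 = 3.1% per episode, and at most 3/60 = 5% of patients. There is no split by arm or severity. The count is per transfusion episode, so it may miss transfusions that were never given.

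**Removal.** If each threshold event carries violation probability v, a patient with k events is removed with probability 1 - (1 - v)^k. At v = 3.1% this is 6% for k = 2 and 15% for k = 5.

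**Illustrative model, no true effect.** These inputs are assumptions, not from the documents: 55% mild patients with 20% poor outcome and 45% severe with 65%, so overall 0.55 × 0.20 + 0.45 × 0.65 = 40.25%. Retained risk in an arm = Σ(weight × retention × risk) / Σ(weight × retention). With v = 3%:

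| Case | Liberal k (mild, severe) | Restrictive arm | Removed, liberal / restrictive | Retained risk, liberal / restrictive | Difference | RR |
|---|---|---|---|---|---|---|
| Low | 1.5, 3.5 | k = 0.3, 1 | 7.0% / 1.9% | 39.6% / 40.0% | -0.4 points | 0.99 |
| High | 2, 6 | k = 0.5, 2 | 10.8% / 3.5% | 38.9% / 39.7% | -0.8 points | 0.98 |
| High, with severity-related restrictive removal | 2, 6 | 4% of mild and 15% of severe removed | 10.8% / 9% | 38.9% / 38.9% | 0.0 | 1.00 |

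Line for the high liberal case: (0.45 × 0.97^6 × 0.65 + 0.55 × 0.97^2 × 0.20) / (0.45 × 0.97^6 + 0.55 × 0.97^2) = 0.347/0.892 = 0.389.

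**Second model, different assumptions.** 40% severe, poor outcome 65% severe and 23% other, and 5 vs 2 liberal-arm events, again with no true effect. At v = 3.1% the RR is 0.98 if 1% of the restrictive arm is removed regardless of severity. It is 1.02 if 20% of severe and 5% of other restrictive patients are removed. In the first of these cases, a simulation with 359 per arm rejected in 5.8% of runs against a nominal 5%.

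**Higher assumed rates.** In the first model (low to high k), v = 6% gives -0.9 to -1.7 points and v = 10% gives -1.5 to -2.8 points (RR 0.96 to 0.93). The last case removes 1 - (0.55 × 0.9^2 + 0.45 × 0.9^6) = 31.5% of the liberal arm.

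**Scale.** The 95% half-width for a risk difference at 359 per arm and 40% risk is 1.96 × √(2 × 0.4 × 0.6 / 359) ≈ 7 points.

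**The case against.** A reader might infer that the patients who leave are the sicker ones, mostly from the liberal arm, and so that the per-protocol result will flatter the liberal strategy. The documents do not support that.

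- Nothing in them says who violates, in which arm, or how ill they were.
- The stated link between grade and anemia does not show that, among patients who are all anemic at entry, worse grade brings more threshold events.
- Events stop at death or discharge, so the earliest deaths have few chances to violate and tend to stay in.
- Restrictive patients transfused above 85 g/L also leave, need not have crossed 80 g/L, and may be sicker, although symptomatic anemia is exempt.

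The larger figures also lack support. The pilot's 97 episodes in 60 patients are 1.6 per patient, near the low case (average 1.5) and below the high case (average 2.5). No document gives a violation rate of 6% or 10%. The possible undercount of omitted transfusions leaves a higher rate open but does not establish one.

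Much is already in place: intention-to-treat is primary, the per-protocol result is supplementary with its population described, violations per patient are counted, and an age- and WFNS-adjusted intention-to-treat estimate is planned. Keeping the primary model on the per-protocol set is also defensible, because then only the population changes.

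All of this limits the size of the point. It does not remove the structural gap: describing an imbalance does not correct the estimate, and an unknown direction makes the unadjusted result harder to read.

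**Conclusion.** The point holds as a modest one. The exclusion is post-randomisation, triggered by a single violation and governed by rules that differ by arm. It is analysed without the prognostic covariates that the SAP already uses elsewhere. Confounding by severity is possible; its direction and size are not established.

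At the pilot rate, and under the stated assumptions, the spurious difference is about -0.4 to -0.8 points against a 10-point target, well inside the sampling error. It is zero or reversed under equally plausible restrictive-arm removal. Larger values rest on violation rates that the documents do not support.

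Two further readings should be resisted. The primary result is not in doubt. Nor would adjustment be a complete cure: in these models stratifying by severity restores a risk ratio of 1.00, but only because severity was made the sole driver of selection.

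**What to change.** In SAP 3.3, 5.2 and Table 4:

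- Specify that the per-protocol analysis of the primary outcome is also fitted with age and WFNS in addition to centre and sex, in the model form already planned for the adjusted sensitivity analysis.
- Print it beside the planned age- and WFNS-adjusted intention-to-treat estimate, so that the two differ only in population.
- Report the number removed by arm, by reason (early transfusion, omission, timing) and by WFNS grade.
- State that the per-protocol comparison is non-randomised and that baseline adjustment does not remove selection driven by the course after randomisation.

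To make the counts by reason interpretable, reconcile the 24-hour timing violation in SAP 3.2, which names no arm, with SAP 2.1, which leaves restrictive-arm timing to the treating team.

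The cost is SAP wording, one extra supplementary model and one table. Both covariates are already collected. The change should be dated before database lock; if made later, it should be labelled post hoc. The remaining limitation is residual confounding by post-randomisation events.
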